10.4. Criteria for Potentially Clinically Significant Values (PCSV)

Parameter	PCSV
Clinical chemistry	
ALT	By distribution analysis: >2 ULN and baseline ≤ 2 ULN >3 ULN and baseline ≤ 3 ULN >5 ULN and baseline ≤ 5 ULN >10 ULN and baseline ≤ 10 ULN >20 ULN and baseline ≤ 20 ULN
AST	By distribution analysis: >2 ULN and baseline ≤ 2 ULN >3 ULN and baseline ≤ 3 ULN >5 ULN and baseline ≤ 5 ULN >10 ULN and baseline ≤ 10 ULN >20 ULN and baseline ≤ 20 ULN
Alkaline Phosphatase	> 1.5 ULN and baseline ≤ 1.5 ULN
Total Bilirubin	> 1.5 ULN and baseline ≤ 1.5 ULN > 2 ULN and baseline ≤ 2 ULN
Conjugated bilirubin	> 35% total bilirubin (when total bilirubin >1.5 ULN)
ALT and Total Bilirubin	ALT > 3 ULN and Total Bilirubin > 2 ULN and baseline ALT ≤ 3 ULN or Total bilirubin ≤ 2 ULN
CPK	> 3 ULN and ≤ 5 ULN and baseline ≤ 3ULN >5 ULN and ≤ 10 ULN and baseline ≤ 5 ULN >10 ULN and baseline ≤ 10 ULN
Creatinine	≥ 150 μmol/L (adults) ≥ 30% from baseline ≥ 100% from baseline
CLcr (mL/min) (Estimated creatinine clearance based on the Cockcroft-Gault equation)	≥15 - <30 (severe decrease in GFR) ≥30 - < 60 (moderate decrease in GFR) ≥60 - <90 (mild decrease in GFR) ≥ 90 (normal GFR)
eGFR (mL/min/1.73m2) (Estimate of GFR based on an MDRD equation)	≥15 - <30 (severe decrease in GFR) ≥30 - < 60 (moderate decrease in GFR) ≥60 - <90 (mild decrease in GFR) ≥ 90 (normal GFR)

Parameter	PCSV
Uric Acid Hyperuricemia: Hypouricemia:	>408 µmol/L <120 µmol/L
Blood Urea Nitrogen	≥17 mmol/L
Chloride	<80 mmol/L >115 mmol/L
Sodium	≤129 mmol/L ≥ 160 mmol/L
Potassium	< 3 mmol/L ≥ 5.5 mmol/L
Glucose Hypoglycaemia Hyperglycaemia	≤ 3.9 mmol/L and < LLN ≥ 7 mmol/L (fasted); ≥ 11.1 mmol/L (unfasted)
HbA1c	>8%
Albumin	≤25 g/L
Hs-CRP	> 2 ULN or >10 mg/L, if ULN not provided
Hematology	
WBC	< 3.0 Giga/L (3000/ mm ³) (Non-Black) < 2.0 Giga/L (2000/ mm ³) (Black) ≥16.0 Giga/L (16000/ mm ³)
Lymphocytes	>4.0 Giga/L
Neutrophils	< 1.5 Giga/L (1500/ mm ³) (Non-Black) < 1.0 Giga/L (1000/ mm ³) (Black)
Monocytes	>0.7 Giga/L
Eosinophils	> 0.5 Giga/L (500/ mm ³) or > ULN if ULN ≥ 0.5 Giga/L
Hemoglobin	≤115 g/L (Male); ≤95 g/L (Female) ≥185 g/L (Male); ≥165 g/L (Female) Decrease from Baseline ≥15 g/L Decrease from Baseline ≥20 g/L
Hematocrit	≤0.37 v/v (Male) ; ≤0.32 v/v (Female) ≥0.55 v/v (Male) ; ≥0.5 v/v (Female)
RBC	≥6 Tera/L

Parameter	PCSV
Platelets	< 100 Giga/L (100 000/mm ³) ≥700 Giga/L (700000/mm ³)
Urinalysis	
pH	≤4.6 ≥8
Vital signs	
HR	≤ 50 bpm and decrease from baseline ≥ 20 bpm ≥ 120 bpm and increase from baseline ≥ 20 bpm
SBP	≤ 95 mmHg and decrease from baseline ≥ 20 mmHg ≥ 160 mmHg and increase from baseline ≥ 20 mmHg
DBP	Young and elderly patients ≤ 45 mmHg and decrease from baseline ≥ 10 mmHg ≥ 110 mmHg and increase from baseline ≥ 10 mmHg
Orthostatic Hypotension	SBP St – Su ≤ - 20 mmHg DBP St – Su ≤ - 10 mmHg
Weight	≥5% increase versus baseline ≥5% decrease versus baseline
ECG parameters	
HR	≤ 50 bpm and decrease from baseline ≥ 20 bpm ≥ 120 bpm and increase from baseline ≥ 20 bpm
PR	≥220 ms and increase from baseline ≥20 ms
QRS	≥ 120 ms
QTc Borderline Prolonged* Additional	Absolute values (ms) Borderline 431-450 ms (Male) 451-470 ms (Female) Prolonged* > 450 ms (Male) > 470 ms (Female) QTc ≥500 ms Increase versus baseline (Males and Females) Borderline Δ 30-60 ms Prolonged * Δ > 60 ms

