Statin can reduce LDL-C by more than 50% in other hypercholesterolemic patients, in HoFH patients; however, statins may provide a decrease of <15 to 30% (Crestor 2003) (Lipitor 1996) (Zocor 1991). When ezetimibe is added to a statin, LDL-C may be reduced by 21 to 27% (Zetia 2002), but many patients with HoFH treated with a high dose statin and ezetimibe remain far from their target LDL-C. Despite the near total loss of functional LDL receptors in HoFH patients, statins are still used as first line therapy in order to maximize residual receptor activity (Raal 2000) (Marais 2008) (Raal 1997).

Mipomersen and lomitapide have been approved in some countries for use in patients with HoFH, and provide an additional ~25% and 40% reduction in LDL-C, respectively, when used along with other lipid-modifying therapies (LMT). However, these new therapies are not commercially available in all countries, and are associated with increases in hepatic fat content and liver function tests, and frequent injection site reactions (mipomersen) or gastrointestinal side effects (lomitapide) that can impact tolerability (Raal 2010, Cuchel 2013).

While PCSK9 inhibitor antibody therapy may provide modest efficacy in the treatment of many patients with HoFH patients with hypercholesterolemia, it appears to be minimally effective in patients with impaired LDL-receptor activity, particularly those patients with null mutations in both LDLR alleles (Raal 2014).

In the recent TESLA study comparing evolocumab on top of statins (with or without ezetimibe) in patients with HoFH, the mean percent reduction in LDL-C at week 12 was 23.1% (Raal 2014).

Evolocumab therapy did not reduce LDL-C in patients with LDL receptor-negative mutations in both alleles (Raal 2014) (Repatha 2015).

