10.4.4.2. Other Safety

Definitions

The following definitions will be applied to laboratory parameters and vital signs:

- The potentially clinically significant value (PCSV) criteria are defined as abnormal values considered medically important by the sponsor according to predefined criteria/thresholds based on literature review and defined by the sponsor for clinical laboratory tests and vital signs. Potentially clinically significant value criteria will be provided in the SAP.
- PCSV criteria will determine which patients had at least 1 PCSV during the respective open-label TEAE period, taking into account all evaluations performed during this period, including unscheduled or repeated evaluations. The number of all such patients will be the numerator for the PCSV percentage.
- Open-label treatment period (OLTP): The treatment period used for quantitative analysis of laboratory and vital signs data in the open-label study period is defined from the day after the first dose of open-label study treatment to the day of the last dose of open-label study treatment + 28 days.

Analysis

Summary statistics of raw data and change from baseline in all continuous laboratory variables (excluding variables in lipid panel) and all vital signs parameters will be presented for each protocol-scheduled visit assessed during the OLTP period.

For selected parameters, mean changes from baseline with the corresponding standard error may be plotted over time (at same time points).

Number and percentage of patients with a potentially clinically significant value (PCSV) at any time point during the open-label TEAE period will be summarized regardless of the baseline level, and again according to the following baseline categories:

- Normal/missing
- Abnormal according to PCSV criterion or criteria

For laboratory parameters for which a PCSV criterion is not defined, similar table(s) using the normal range will be provided, regardless of baseline level.

Listings will be provided with flags indicating the out of laboratory range values.

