2.2. Sample Size and Power Considerations

Since this study is an open-label single treatment arm study for patients with HoFH, no calculation for sample size was performed. Approximately 120 patients will be enrolled.

[figure not shown]
To gain experience with evinacumab in the subpopulation of adolescent patients, this study will plan to enroll approximately 14 patients in the age range of 12 years to < 18 years old. Due to the rare patient population planned for evaluation, the sample size of 14 patients was chosen for practical reasons, centered on the feasibility to identify and enroll these patients into the trial and regulatory precedent.

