5.8.3. Clinical Laboratory Measurements

Clinical laboratory parameter actual values (quantitative) and change from baseline values will be descriptively summarized at baseline and each post-baseline visit for the open-label treatment (OLTP) period, by at least patient number, mean, median, Q1, Q3, SD, minimum and maximum.

Clinical laboratory parameters mean changes from baseline, with the corresponding SE, can be plotted at each visit in the case results warrant further investigation. These parameters will be presented by the biological functions defined in Section 4.8.2. For glucose, only fasting samples will be included in the summaries.

Individual patient laboratory parameter measurements will be additionally evaluated by PCSV criteria (See Appendix 10.4), specifically identifying patients with at least one post-baseline measurement that meets the PCSV criteria within the TEAE period. These laboratory parameters will be presented by the biological functions defined in Section 4.8.2. The incidence of PCSVs at any time during the TEAE period will be summarized regardless of the baseline level, and again according to the following baseline categories:

- Normal (according to PCSV criterion/criteria)/missing
- Abnormal according to PCSV criterion or criteria

Patient listings of laboratory measurements that meet PCSV criteria will be provided for the report appendix.

For those laboratory parameters that don't have an associated PCSV criteria, similar summary tables can be provided based on measurements outside the central laboratory normal ranges, if applicable.

Drug-induced liver injury

For the treatment period, an evaluation of drug-induced serious hepatotoxicity (eDISH) with the graph of distribution of peak values of ALT versus peak values of total bilirubin will also be presented using post-baseline values during TEAE period. Note that the ALT and total bilirubin values are presented on a logarithmic scale. The graph will be divided into 4 quadrants with a vertical line corresponding to 3 x ULN for ALT and a horizontal line corresponding to 2 x ULN for total bilirubin.

Patient listing of possible Hy's law cases identified by patient group (i.e., patients with any elevated ALT > 3 x ULN, and associated with an increase in bilirubin > 2 x ULN, concomitantly or not) with ALT, AST, ALP, total bilirubin, and if available direct and indirect bilirubin will be provided.

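### The baseline clause in the ALT, AST, ALP, total bilirubin and CPK criteria conflicts with the planned PCSV rows for all patients and for patients abnormal at baseline

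*SAP*

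**What the plan says.** SAP 10.4 gives ALT and AST five tiers (2, 3, 5, 10 and 20 x ULN), for example ">3 ULN and baseline ≤ 3 ULN". ALP has one tier, "> 1.5 ULN and baseline ≤ 1.5 ULN". Total bilirubin has two (1.5 and 2 x ULN). CPK has three bands, the middle one being ">5 ULN and ≤ 10 ULN and baseline ≤ 5 ULN". In each, the baseline must lie at or below the lower bound of that tier. Two liver criteria differ. Conjugated bilirubin, "> 35% total bilirubin (when total bilirubin >1.5 ULN"), has no baseline clause, and the combined ALT and bilirubin rule joins its two baseline conditions with 'or'.

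SAP 5.8.3 has the PCSV incidence "summarized regardless of the baseline level, and again according to the following baseline categories"; the categories are normal or missing, and abnormal by the PCSV criterion or criteria. Protocol 10.4.4.2 plans the same: the number and percentage of patients with a PCSV "will be summarized regardless of the baseline level", then by baseline category. SAP 5.8 sets the denominator as every patient assessed for the parameter at least once in the TEAE period. SAP 1.2.3 declares no departure from the protocol's statistical section.

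**The concern.** The tables are meant to show three things: how many patients had a PCSV at all, how many of those started normal, and how many started abnormal. A definition that already excludes patients above the threshold at baseline cannot fill the third row, and it turns the first into a copy of the second. A reader who sees 0% among patients with abnormal baselines may take it as an observation, when no other value was possible.

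Laboratory safety belongs to the primary endpoint. SAP 10.3 also uses laboratory PCSVs as a source for two adverse events of special interest, hepatic disorders and muscle events/CK elevation, and the SAP 5.8.3 listing of values meeting PCSV criteria inherits the same exclusion. Abnormal liver baselines are plausible: Protocol 7.7.1 permits lomitapide and mipomersen, which Protocol 1 says "are associated with increases in hepatic fat content and liver function tests".

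**Working it through.** There is no planned figure to reproduce; SAP 2.2 states that "no calculation for sample size was performed". The check is one of logic. Let B be the baseline and P a value on treatment, both in multiples of ULN, and t the lower bound of a tier (u its upper bound, for the lower two CPK bands).

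**1. The abnormal row.** A tier is met when P > t (and P ≤ u where there is one) and B ≤ t. Abnormal at baseline on that tier means B > t. Both cannot hold, so the count is 0. Enumerating B and P from 0.1 to 30 x ULN in steps of 0.1 gave no flagged combination with B > t in any of the 5 + 1 + 2 + 3 = 11 tiers (ALT/AST, ALP, bilirubin, CPK).

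**2. The overall row.** Overall count = normal/missing count + abnormal count = normal/missing count + 0. The denominator is still all assessed patients.

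**3. Which rises are counted.**

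| Test | Baseline to peak (x ULN) | Ratio | Any tier met? |
|---|---|---|---|
| ALP | 1.6 to 6 | 3.75 | No |
| Total bilirubin | 2.1 to 8 | 3.81 | No |
| Total bilirubin | 1.6 to 2.4 | 1.50 | Yes (>2) |
| ALT/AST | 3.2 to 4.9 | 1.53 | No |
| ALT/AST | 5.5 to 9.9 | 1.80 | No |
| ALT/AST | 2.5 to 4 | 1.60 | Yes (>3) |
| CPK | 5.5 to 9.9 | 1.80 | No |
| CPK | 11 to 28 | 2.55 | No |
| CPK | 4 to 7 | 1.75 | Yes (>5 to 10) |
| CPK | 4 to 12 | 3.00 | Yes (>10) |

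Over the grid, the worsening pairs that start above the lowest tier and meet some tier number 0 of 40,470 for ALP, 1,400 of 40,470 for bilirubin, 15,000 of 36,315 for CPK and 27,700 of 39,060 for ALT/AST. These counts describe the rules, not patient frequencies.

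**4. The combined rule.** With ALT 5 and bilirubin 3 x ULN on treatment, it is met from baselines of ALT 4/bilirubin 1 and ALT 1/bilirubin 3, but not from ALT 4/bilirubin 3. Only patients abnormal on both are excluded.

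**5. Per tier or any tier.** If baseline abnormality means exceeding any tier, the abnormal row can be non-zero for the higher ALT, AST, bilirubin and CPK tiers. The lowest tier of each test, and so ALP altogether, stays at zero. The SAP does not say which reading applies.

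**6. Size, on assumed inputs.** Take 120 patients, k abnormal at baseline, and an event risk of 5% from a normal baseline. As written, the overall row shows (120 − k) × 0.05/120. Without the clause it shows [(120 − k) × 0.05 + k × r]/120, where r is the risk from an abnormal baseline. I use r = 50%.

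| k | As written | Without clause | Abnormal row: as written, then expected without clause |
|---|---|---|---|
| 2 | 5.9/120 = 4.92% | 6.9/120 = 5.75% | 0/2, then 1/2 |
| 6 | 5.7/120 = 4.75% | 8.7/120 = 7.25% | 0/6, then 3/6 |
| 12 | 5.4/120 = 4.50% | 11.4/120 = 9.50% | 0/12, then 6/12 |

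If r were also 5%, the figure without the clause would be 5.00% for every k. The denominator effect alone is k/120: 1.7%, 5% and 10% relative, or 0.08, 0.25 and 0.50 percentage points.

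**7. Who could be affected.** Protocol 6.2.2 (#11) excludes evinacumab-naïve patients with ALT, AST or CPK above 3 x ULN at screening, so ALT/AST between 2 and 3 x ULN remains possible. Neither exclusion list limits ALP or bilirubin. For R1500-CL-1629 patients, SAP 6.1 takes the baseline from before the first double-blind dose of that study.

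**The case against.** The best defence is that these are new-onset criteria by design, and that the row layout is a common template. It works for parameters such as sodium or urea nitrogen, whose criteria have no baseline clause. That explains how the conflict arose but does not remove it: neither SAP 5.8.3 nor SAP 10.4 exempts the five tests. If new onset is intended, the overall row is mislabelled, the abnormal row has no meaning and the denominator should be the patients at risk.

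The second defence is that these patients are visible elsewhere, and much of this stands. SAP 5.8.3 summarises actual values and change from baseline, with maxima, by visit. Protocol 10.4.4.2 plans listings that flag out-of-range values. Protocol 9.4.3 makes ALT or AST of at least 2 x baseline, from a baseline at or above ULN, a reportable event of special interest. SAP 10.3 adds MedDRA queries for hepatic and muscle events, and the eDISH plot and Hy's law listing for ALT and bilirubin carry no baseline condition. What is missing is a count of patients above threshold that does not depend on baseline, notably for AST, ALP and CPK.

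Third, all safety summaries are descriptive, and the dilution in step 6 amounts to less than one patient in 120. That is fair for the overall row. It does not repair a row that can print only zero.

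**Conclusion.** The definitions and the tables contradict each other, and the result printed would be wrong as labelled. For ALP this holds under any reading. For ALT, AST, total bilirubin and CPK it holds tier by tier when baseline is judged at the same threshold. Severity is moderate: partial cover exists and the number of patients concerned is unknown.

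Four stronger inferences are tempting but not supported:

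- **All worsening from an abnormal baseline is lost.** Rises into a higher tier are counted (step 3).
- **Every liver criterion is affected.** Conjugated bilirubin is not, and the combined rule only partly is.
- **Patients from previous studies enter with no limit because Protocol 6.2.3 has no laboratory criteria.** For R1500-CL-1629 patients, which Protocol 1 describes as most of the continuing patients, that section does not govern the baseline used, and the parent study's entry limits are not in these documents. R1500-CL-1331 patients do use the baseline of this study, but Protocol 1 reports only 9 treated there.
- **A known share, such as 5% to 10%, is abnormal at baseline.** The documents give no such figure; the values in step 6 are assumptions.

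**What to change.** Amend SAP 10.4 and 5.8.3 before database lock in one of two ways.

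- **Preferred.** For the overall and abnormal-baseline rows, define the ALT, AST, ALP, total bilirubin and CPK PCSVs by the on-treatment threshold alone. Keep the baseline clause only in the normal/missing row, where it defines new onset.
- **Alternative.** Keep the clause as it is, drop the abnormal-baseline row for these tests, restrict denominators to patients at risk, and add a shift table from baseline to worst value on treatment.

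In either case, state whether baseline abnormality is judged per tier or on any tier. If a row for worsening relative to baseline is wanted, limit a criterion of at least 2 x baseline to ALT and AST, where Protocol 9.4.3 already uses it. The documents give no basis for that multiple in ALP, bilirubin or CPK. It would also miss rises such as ALT 3.2 to 4.9 x ULN (ratio 1.53), so it cannot replace the shift table.

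The cost is SAP wording and some table programming, with no new data. Under the preferred option the overall percentages will rise somewhat and will include elevations that merely persist from baseline; the rows by baseline status, or a shift table, separate these.

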5.8. Analysis of Safety Data

Safety summaries for the study will be presented by patient group for the study in the safety analysis set, and again for the subpopulation of adolescent patients. No formal inferential testing will be performed. Summaries will be descriptive in nature.

All safety analyses will be performed using the baseline definitions described in Section 6.1.

General common rules

All safety analyses will be performed, unless otherwise specified, using the following common rules:

- Safety data in patients who do not belong to the safety analysis set (e.g., exposed but not enrolled) will be listed separately.
- The potentially clinically significant value (PCSV) values are defined as abnormal values considered medically important by the Sponsor according to predefined criteria/thresholds based on literature review and defined by the Sponsor for clinical laboratory tests and vital signs (PCSV version dated January 2009 [Appendix 10.4]).

Considering that the threshold defined in the PCSV list for monocytes and basophils can be below the ULN, the following PCSV criterion will be used for the PCSV analysis of monocytes and basophils:

- PCSV criterion for monocytes: >0.7 Giga/L or >ULN (if ULN ≥0.7 Giga/L).
- PCSV criterion for basophils: >0.1 Giga/L or >ULN (if ULN ≥0.1 Giga/L).

- PCSV criteria will determine which patients had at least 1 PCSV during the TEAE period, taking into account all evaluations including unscheduled or repeated evaluations.
- The treatment-emergent PCSV denominator by patient group for a given parameter will be based on the number of patients assessed for that given parameter at least once during the TEAE period.
- All measurements, scheduled or unscheduled, fasting or not fasting, will be assigned to Global Analysis Windows defined in Appendix 10.2 /Table 1 in order to provide an assessment for the screening visit through follow-up visit time points.
- For quantitative safety parameters including central laboratory measurements and vital sign scores, descriptive statistics will be used to summarize observed values and change from baseline values by visit.
- Open-label treatment period (OLTP): The treatment period used for quantitative analysis of laboratory and vital signs data in the open-label study period is defined from the day after the first dose of open-label study treatment to the day of the last dose of open-label study treatment + 28 days.

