The summary of clinical laboratory parameter measurements will be provided for all patients in the study in the safety analysis set, and again for the subpopulation of adolescent patients.

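### In SAP 10.4 the CLcr and eGFR rows have no class below 15 and list normal GFR (≥90) as a PCSV, so those rows cannot be applied as written

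*SAP*

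**What the plan says.** The PCSV table in SAP 10.4 has a CLcr row ("Estimated creatinine clearance based on the Cockcroft-Gault equation") and an eGFR row ("Estimate of GFR based on an MDRD equation"). Both carry the same four entries in the PCSV column: "≥15 - <30 (severe decrease in GFR) ≥30 - < 60 (moderate decrease in GFR"), then "≥60 - <90 (mild decrease in GFR) ≥ 90 (normal GFR"). Neither row has an entry below 15, a condition on baseline, or an age rule.

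SAP 5.8 says that PCSVs "are defined as abnormal values considered medically important by the Sponsor according to predefined criteria/thresholds". It counts a patient who has one or more in the treatment-emergent period. The denominator is the patients assessed for that parameter at least once in that period.

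SAP 5.8.3 repeats the rule for laboratory data, "specifically identifying patients with at least one post-baseline measurement that meets the PCSV criteria within the TEAE period". It then splits the incidence by baseline status. Normal (pooled with missing) and abnormal are both judged by the same PCSV criteria. The laboratory summaries are given for all patients and "again for the subpopulation of adolescent patients".

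The same appendix has other renal criteria. Creatinine is flagged at 150 µmol/L or more (marked as applying to adults) and at "≥ 30% from baseline ≥ 100% from baseline", with no age limit on the relative changes. Blood urea nitrogen (BUN) is flagged at 17 mmol/L or more. SAP 4.8.2 lists the renal function group as creatinine, BUN and uric acid. It does not mention CLcr or eGFR.

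**The concern.** A PCSV list should pick out abnormal values. For GFR the printed list does the opposite at both ends: the most abnormal values match nothing and normal values match an entry. The baseline split inherits the same inversion.

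Safety is the primary endpoint, and adolescent safety is a primary objective. A safety scale that contradicts its own definition leaves the programmer to guess which entries count. The result could be a GFR table in which normal values are counted as findings and the worst values have no line.

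**Working it through.** There is no sample size, power or error rate to reproduce. Two checks apply.

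**1. The printed classes under the SAP's own rules.** The inputs are the four classes in SAP 10.4, the counting rule in 5.8 and the baseline split in 5.8.3.

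| GFR test values | Class matched | Counts as PCSV | Baseline group |
|---|---|---|---|
| 5, 10, 14.9 | none | no | Normal/missing |
| 15, 29.9 | severe decrease | yes | Abnormal |
| 30, 59.9 | moderate decrease | yes | Abnormal |
| 60, 89.9 | mild decrease | yes | Abnormal |
| 90, 120 | normal | yes | Abnormal |

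If the classes are combined, 100% of assessed patients have a PCSV, unless all of a patient's post-baseline values are below 15. The normal/missing baseline group holds only patients with GFR below 15 or no value. If the classes are tabulated one by one, the normal line is merely mislabelled. The missing line below 15 and the inverted baseline split remain.

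**2. Would another criterion catch a fall below 15?** The documents do not give the equations in full, so this step rests on assumptions. GFR is taken as proportional to creatinine^(−k), with the patient's other inputs held fixed. Here k = 1 for Cockcroft-Gault and k = 1.154 for MDRD. The creatinine rise for a fall from baseline b to 15 is (b/15)^(1/k) − 1.

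| Baseline b | Rise, k = 1 | Rise, k = 1.154 |
|---|---|---|
| 90 | 6 − 1 = 500% | 372% |
| 60 | 4 − 1 = 300% | 232% |
| 30 | 2 − 1 = 100% | 82% |
| 20 | 1.33 − 1 = 33% | 28% |
| 18 | 1.2 − 1 = 20% | 17% |

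The 30% criterion can fail at a GFR just under 15 only if baseline was already below 15 × 1.3 = 19.5 (k = 1) or 15 × 1.3^1.154 = 20.3 (k = 1.154).

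In adults the absolute threshold closes that gap. With an MDRD constant of 175, a GFR of 15 corresponds to creatinine of 268 to 447 µmol/L at ages 18 to 75, both sexes. With Cockcroft-Gault it corresponds to 181 to 899 µmol/L at the same ages and weights of 40 to 90 kg. All of these exceed 150 µmol/L.

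What remains is an adolescent whose baseline creatinine is missing or whose baseline GFR was already about 20 or lower. There the adult threshold does not apply and the relative change is absent or may be too small. BUN may still flag such a patient.

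**The case against.** The strongest reply has three parts.

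First, the labels run from severe to normal, so the rows may be meant as a category distribution. A line labelled normal cannot be a PCSV when SAP 5.8 defines PCSVs as abnormal. That may well be the intent, but the SAP does not say so. The ALT and AST entries in the same table are marked as a distribution analysis and carry baseline conditions. The GFR entries have neither, and nothing states which of them count.

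Second, a GFR table may never be produced. SAP 5.8.3 presents laboratory parameters by the functional groups of 4.8.2, which omit CLcr and eGFR. The protocol's chemistry panel (8.2.2.5) omits them too. This stands: near-universal GFR PCSVs are what the rules would give if the rows are used, not a certain output. It is also an inconsistency to settle.

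Third, the creatinine and BUN criteria already protect patients. This stands as well. A reader might infer that the renal safety tables as a whole would miss renal failure. The second check does not support that, because nearly every true fall below 15 would be flagged elsewhere.

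A reader might also infer that the two equations are wrong for patients aged 12 to <18. The documents do not say for which ages either equation is valid, and they do not identify the MDRD version. They show only that the absolute creatinine threshold is marked for adults while the GFR rows state no age rule.

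**Conclusion.** The point holds for the CLcr and eGFR rows of SAP 10.4. Read with 5.8 and 5.8.3, they count every value of 15 or more as a PCSV and as abnormal at baseline, and count no value below 15. This follows from the text alone and contradicts the SAP's definition.

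The consequence is modest. All the affected summaries are descriptive, no inference depends on them, and the creatinine criteria catch nearly all true falls below 15. That last statement rests on the assumed exponents of 1 and 1.154, the assumed MDRD constant, and the age and weight ranges shown. The correction is worth making because the rule is wrong as printed and cheap to repair.

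**What to change.** In SAP 10.4, add a class below 15 to both the CLcr and eGFR rows. Keep 90 and above only as a normal reference category, and state that it is not a PCSV, either for the incidence count or for the baseline normal/abnormal split in 5.8.3. The classes then cover all values, and the PCSV range becomes GFR below 90 instead of GFR of 15 and above.

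Reconcile SAP 4.8.2 with 10.4: either add CLcr and eGFR to the renal function group, or say that they are not tabulated. State whether the GFR rows apply at ages 12 to <18, since the neighbouring creatinine threshold is limited to adults.

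The cost is a few lines of SAP text and a small programming change. SAP section 1 allows revision before database lock. No new data are needed, and the sample size does not change.
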